5.1.1 Study Duration

This is an 8 week pilot RCT.

The study has received 50 doses of in-kind Sublocade™ study medication from the manufacturer, Indivior as of September 13, 2019. With this new stock of medication, we would like to offer all participants the option of a therapeutic treatment extension of 24 weeks post study visit 5 week 8. Active treatment will continue after the Week 8 study visit through Week 20 wherein participants will be eligible to receive initial and/or additional XRB injections. A safety visit, in which no medication is administered, will be conducted at Week 24 to document safety reporting and provide post-study treatment referrals.

This 24 week therapeutic extension will be offered to all interested participants regardless of their treatment assignment after the completion of Visit 5 Week 8. Only Sublocade™ injections will be offered, no additional forms of compensation will be provided.

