5.3.2 Eligibility Criteria/Vulnerable Populations

Inclusion criteria

- 1) Adults ≥ 18 yo incarcerated in NYC jails with known release dates.
- 2) DSM-V criteria for current opioid use disorder (DSM-IV opioid dependence).
- 3) Currently maintained on sublingual buprenorphine-naloxone in the NYC jail opioid treatment program.

Exclusion Criteria

- 1) Individual not interested in XRB treatment. Current SLB patients are otherwise by definition appropriate for XRB.
- 2) Pregnant or planning conception. As female participants are incarcerated & active in the jail opiate treatment program at the time of baseline assessments and treatment induction, a pregnancy test is not required by the study staff. A urine dipstick pregnancy (hCG) test will be administered at week 4 visit 3. The test detects human chorionic gonadotropin (hCG) in urine with a sensitivity/specificity of: 25 mIU hCG/ml, >99%. Time to result is four minutes. If negative, a urine pregnancy test will be administered at the final week 8 visit 5 and final week 20 visit 8 (if applicable) to ensure that a participant is not pregnant.
- 3) No severe or acute medical or psychiatric disability preventing safe study participation or making follow-up unlikely.

Federal Research among Prisoners. Study participants are clearly considered prisoners at the time of enrollment. The NYU SOM IRB will contact DHS/OHRP to address this topic and for permission to enroll prisoners in a federally funded research trial. However, we believe this study carefully conforms to the Federal guidelines for research among prisoners (CFR 46.306) in the following manner:

1.) Research on practices, both innovative and accepted, which have the intent and reasonable probability of improving the health or well-being of the subject. In cases in which those studies require the assignment of prisoners in a manner consistent with protocols approved by the IRB to control groups which may not benefit from the research, the study may proceed only after the Secretary has consulted with appropriate experts, including experts in penology medicine and ethics, and published notice, in the Federal Register, of his intent to approve such research.

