(7) Where the Board finds there may be a need for follow-up examination or care of participants after the end of their participation, adequate provision has been made for such examination or care, taking into account the varying lengths of individual prisoners' sentences, and for informing participants of this fact. The study primarily consists of community follow-up of adults released from NYC jails. Follow-up consists of research visits conducted weekly then bi-weekly for both medication arms post-release (week 1 post-release, week 2, week 4, week 6, week 8). After the completion of Visit 5 Week 8, all participants will be eligible for a 24 week therapeutic extension study wherein they are offered initial and/or additional XRB injections. These will occur monthly post study week 8: week 12, week 16, week 20, week 24, and week 28. A final safety visit, no medication administered, will be conducted at week 32 to document safety reporting and provide post-study treatment referrals.

6 - Methods

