6.1.2 Dosage, Admin, Schedule

Buprenorphine Extended Release: XRB is a 300mg or 100mg pre-mixed subcutaneous injectable formulation to be administered monthly. XRB is for abdominal subcutaneous injection only. Participants in the XRB treatment arm will be given 1 or more XRB injections prior to release from jail and one or more at weeks 4, 8, 12, and 16 post-release, depending on their release date.

Sublingual Buprenorphine: SLB (SUBOXONE, Zubsolv, or generic tablets) is a daily sublingual film or tablet ranging from 8-24mg/day or equivalent (Zubsolv is dosed 5.7-17.1 mg/day). The film or tablet is placed under the tongue for 5 to 10 minutes until dissolved completely. Participants in the SLB treatment arm will be provided SLB daily by observed dosing in-jail (controlled substances are not self-administered in-jail) and encouraged to continue SLB treatment in weekly, bi-weekly, or monthly quantities for unobserved, daily, self-administration through week 5. Patients may obtain SLB care free-of-charge from the Bellevue Hospital Center Addiction Medicine clinic or from non-NYU/Bellevue providers and pharmacies per usual care standards. After the completion of Visit 5 Week 8, SLB participants will be offered XRB treatment in the 20 week therapeutic extension. If interested, participants would receive one or more XRB injections during the period of Weeks 8, 12, 16, 20, 24, and 28 followed by a final safety documentation visit at Week 32.

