Sublingual Buprenorphine: Participants randomized to this arm will be provided SLB daily maintenance per usual Opioid Treatment Programs protocols in-jail. Post-release, SLB arm participants will receive follow-up care at Bellevue Hospital's Addiction Medicine or at non-BHC/NYU community providers, per their preference. We expect and will encourage most participants to follow-up at Bellevue, though this is not mandated. Typically an initial week's supply of SLB is prescribed within one week of release. At visit 2, week 2, SLB participants typically refill a two week's supply of daily maintenance SLB. SLB participants will continue to receive 2-4 week refill prescriptions for SLB from visit 2, week 2 through visit 6, week 8. Regardless of SLB prescribing patterns, they are encouraged to attend study follow-up visits at BHC per the same study schedule (Weeks 1,2,4,6,8). After the completion of Visit 5 Week 8, SLB participants will be offered XRB treatment in the 24 week therapeutic extension. If interested, participants would receive one or more XRB injections during the

period of Weeks 8, 12, 16, 20, 24, and 28 followed by a final safety documentation visit at Week 32.

For both treatment arms, urine toxicology tests will be conducted at all follow-up visits at the BHC Addiction Medicine Clinic in order to detect any illicit substance use as well as buprenorphine adherence.

STUDY SCHEDULE												
Test/Procedures	Screening/ Randomization	Treatment Period & Follow-Up					XR-B 20 Week Treatment & Follow-Up					
Study Visit Number	0	1	2	3	4	5	6	7	8	9	10	11
Week	0	1	2	4	6	8	12	16	20	24	28	32
Informed Consent ¹	X											
HIPAA ²	X											
Locator Form	X											
Medical History	X											
Psychological History	X											
Physician Progress Note	X	X	X	X	X	X	X	X	X	X	X	X
Confirm Eligibility	X											
Randomization	X											
Adverse Event Forms (AE, SAE, BUP specific AE)		X	X	X	X	X	X	X	X	X	X	X
Clinical Assessment of Intervention ³						X						X
Urine Toxicology		X	X	X	X	X	X	X	X	X	X	X
Pregnancy Test				X		X		X			X	
Demographics	X											
MOUD History/Preference	X											
ASI-Modified Lifetime/CJS-Baseline	X											
Timeline Followback	X	X	X	X	X	X	X	X	X	X	X	X
Inmate Lookup Form⁴		X	X	X	X	X						
New Arrests and Days Incarcerated Form⁴		X	X	X	X	X						
Overdose Form		X	X	X	X	X	X	X	X	X	X	X
XR-B Administration Form	X			X			X	X	X	X	X	

NYS Prescription Monitoring Data (SLB- Only)		X	X	X	X	X						

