6.3.5 On Study Visits

Screening and Randomization (~1.5 hours):

- Informed Consent & Informed Consent Quiz
- Baseline assessments:
 - Drug and alcohol use history (ASI-Lite)
 - Pre-arrest recall of drug and alcohol use (Timeline Followback)
 - Prior Medication Treatment for Opioid Use Disorder exposure & preferences (MOUD Preference form)
 - Jail Electronic Medical Record medical and psychiatric history & laboratory data, including HIV and HCV status
- Randomization envelope opened & completed by study staff and participant
 - Medication dispensed (XRB or SLB)
 - *Additional in-jail injections of XRB may occur if participant is incarcerated for over 4 weeks.*

Follow-Up Visits (v1-4, ~1 hour)

- Administrative data for SLB medication refills and post-release XRB injections
- Self-reported opioid and other drug use (Timeline Followback)
- Urine specimen collection and toxicology testing
- Adverse Event and Serious Adverse Event monitoring (SAFTEE)
- NYS Prescription Monitoring Data for community SLB pharmacy refill reporting
 - I-STOP/PMP Registry
- Treatment Retention Form completed
- *At visit 1 week 1, open-ended interview will be administered.*

- *At visit 3 week 4, second XRB administered, depending on prior injection date.*
- *At visit 3 week 4, pregnancy test will be administered..*

Research Visit 5 Week 8 (Final Visit, ~1 hour):

- Medication is not dispensed
- For participants electing to continue in the 24 week extension, initial and/or additional XRB injection could be administered at this time point
- Self-reported opioid and other drug use (Timeline Followback)
- Urine specimen collection and toxicology testing
- Pregnancy testing
- Treatment Retention completed
- Treatment Satisfaction completed
- Adverse Event and Serious Adverse Event monitoring (SAFTEE)
- NYS Prescription Monitoring Data for community SLB pharmacy refill reporting
 - I-STOP/PMP Registry
- Open-ended interview with participants concerning XRB vs. SLB treatment satisfaction and ease-of-use

Treatment Visit 6-10 Week 12, 16, 20, 24, 28 (~1 hour):

- 24 Week Extension Participants Only:
 - Self-reported opioid and other drug use (Timeline Followback)
 - Urine specimen collection and toxicology testing
 - Adverse Event and Serious Adverse Event monitoring (SAFTEE)
 - *XRB administered, depending on prior injection date.*
 - *At visit 7 week 16 and visit 10 week 28, pregnancy test will be administered*

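### After Week 8 the XRB extension has two conflicting pregnancy-test calendars, and no text makes a negative test a condition of injection

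*Combined protocol and SAP*

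**What the plan says.** Section 5.3.2 excludes women who are pregnant or planning conception, and 6.2.2 repeats the exclusion. Women are recruited from the Rose M Singer Center (5.1.2). Section 5.3.2 requires no study test in jail. It asks for an hCG dipstick at Week 4 and, if that is negative, "a urine pregnancy test will be administered at the final week 8 visit 5 and final week 20 visit 8 (if applicable".

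Section 6.3.5, for extension participants, gives other dates: "At visit 7 week 16 and visit 10 week 28, pregnancy test will be administered". The row "Pregnancy Test" of the table in 6.3.1 agrees with 6.3.5. Its marks fall at Visits 3, 5, 7 and 10, which are Weeks 4, 8, 16 and 28. There is none at Visit 8, Week 20.

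On extension injections, item 7 of the prisoner-research list in 5.3.2 says "These will occur monthly post study week 8: week 12, week 16, week 20, week 24, and week 28". For the SLB arm, 6.1.2 says "participants would receive one or more XRB injections during the period of Weeks 8, 12, 16, 20, 24, and 28". At Week 8, under 6.3.5, an "initial and/or additional XRB injection could be administered at this time point". Section 5.1.1 labels the weeks differently: treatment continues "through Week 20 wherein participants will be eligible to receive initial and/or additional XRB injections", with a drug-free safety visit at Week 24.

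Urine is already collected: "For both treatment arms, urine toxicology tests will be conducted at all follow-up visits at the BHC Addiction Medicine Clinic".

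**The concern.** Sections 5.3.2 and 6.3.5 give site staff different instructions for the same visits. Section 5.3.2 also disagrees with itself: it calls the Week 20 test final, yet its item 7 lists injections at Weeks 24 and 28.

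The second gap is that no test result is tied to a dose. The only condition that 6.3.5 puts on an extension injection is the date of the previous one. Section 6.1.7 asks for toxicology at dispensing visits, and 6.1.8 limits route and interval. In 5.3.2 a negative result decides whether later tests are done, not whether XRB is given. No section says what to do after a positive result.

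What is at stake is participant safety and consistent conduct. A woman who conceives after her last test meets a stated exclusion and could still receive a month-long dose. Section 5.3.2 omits the in-jail test because women are then incarcerated and in the jail treatment program; that reason no longer applies once they are released.

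**Working it through.** The plan gives no figure to reproduce, so the check sets the two calendars against the injection visits.

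**Inputs**
- Possible injection visits: Weeks 8, 12, 16, 20, 24 and 28 (6.1.2; Weeks 12 to 28 also in 5.3.2 item 7 and 6.3.5).
- Tests from Week 8 under 5.3.2: Weeks 8 and 20.
- Tests from Week 8 under 6.3.5 and the table: Weeks 8, 16 and 28.

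| Study week | 8 | 12 | 16 | 20 | 24 | 28 |
|---|---|---|---|---|---|---|
| 5.3.2 alone | test | none | none | test | none | none |
| 6.3.5 and table alone | test | none | test | none | none | test |
| Both followed | test | none | test | test | none | test |

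**Visits without a same-visit test**
- 5.3.2 alone: Weeks 12, 16, 24 and 28, so 4 of 6.
- 6.3.5 and table alone: Weeks 12, 20 and 24, so 3 of 6.
- Both followed: Weeks 12 and 24, so 2 of 6.

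Week 8, the entry to the extension, has a test on every reading. The calendars disagree at Weeks 16, 20 and 28, and neither tests at Weeks 12 or 24.

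**Age of the last test at an untested visit** (injection week minus last test week, full attendance)
- 5.3.2 alone: 12 − 8 = 4; 16 − 8 = 8; 24 − 20 = 4; 28 − 20 = 8 weeks.
- 6.3.5 and table alone: 12 − 8 = 4; 20 − 16 = 4; 24 − 16 = 8 weeks.
- Both followed: 12 − 8 = 4; 24 − 20 = 4 weeks.

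**Weeks in 5.1.1.** Counted from Week 8, its Week 20 is study Week 8 + 20 = 28 and its Week 24 is study Week 8 + 24 = 32. These match the last injection and the safety visit in the other sections.

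**The case against.** **One stray clause.** The visit-by-visit procedures and the table agree, and the odd date sits in the eligibility section. That stands, and it makes the date easy to correct. Correcting it alone still leaves Weeks 12, 20 and 24 without a test and leaves dosing without a rule.

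**Staff can do both.** Nothing in 6.3.5 forbids a Week 20 test, so a careful team would miss only Weeks 12 and 24, each 4 weeks after a test. This is a fair lower case. The word final in 5.3.2 fits it poorly, because a Week 28 test would follow.

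**A shorter extension.** A reader might infer from 5.1.1 that dosing once ended at study Week 20 and that the Week 20 test is left over from then. The documents do not establish this. Section 5.1.1 describes a 24-week extension after Week 8, and counting from Week 8 brings it into line with the other sections. Recounting does not rescue 5.3.2, though: it names Visit 8, which the table puts at study Week 20, and the Week 16 test would still be absent.

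**Partial safeguards.** Section 5.3.2 gives confirmation of non-pregnancy as the purpose of testing, 6.2.2 provides physician monitoring and discontinuation where needed, and the table has a physician note at every visit. A clinician could reasonably infer a check before dosing. It is not written as a requirement.

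**Interval testing is a legitimate choice.** No section sets a standard of one test per dose. That stands: the per-dose rule below is a recommendation, chosen because it removes the conflict simply.

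**Conclusion.** The point holds and should be fixed. Between two and four of the six possible extension injection visits have no same-visit pregnancy test, depending on which sections staff follow, and no section links a result to dosing. The counts assume that XRB can be given at each of Weeks 8 to 28; actual visits depend on each woman's previous injection date. The 4-to-8-week ages assume full attendance.

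A reader might infer more than this. Tests 16 weeks old (24 − 8, under 6.3.5 and the table) or 20 weeks old (28 − 8, under 5.3.2) would arise only if a test visit were missed and not made up, which the documents neither plan nor quantify. Nor do they show that any pregnant woman would in practice be injected: the number of women is not stated, and clinicians may check unprompted. The Week 4 retention comparison is unaffected, because the extension begins only after the Week 8 visit.

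**What to change.** 1. Correct the Week 20 Visit 8 date in 5.3.2 and use one rule in 5.3.2, 6.3.5 and the table: at every community visit where XRB is given, run a urine hCG dipstick on the urine already collected and read it before the injection. Mark the table row at Weeks 8, 12, 16, 20, 24 and 28, keeping Week 4.
2. State the action on a positive result: do not give study XRB, and have the study physician arrange same-day linkage to the sublingual buprenorphine or methadone care at Bellevue described in 6.3.6 and 6.3.7. Treatment should not lapse, since 3.3.2 links relapse to death and disability.
3. In 5.1.1, say whether Weeks 20 and 24 are counted from Week 8, that is, whether they mean study Weeks 28 and 32.

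The rule leaves in-jail dosing as 5.3.2 has it.

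**Cost.** Beyond wording, a woman completing the extension needs three extra dipsticks against 6.3.5 and the table (Weeks 12, 20, 24) or four against 5.3.2 (Weeks 12, 16, 24, 28). At the protocol's four minutes each, that is 3 × 4 = 12 or 4 × 4 = 16 minutes in total. Section 6.3.1 also allows community injections from study Week 1. With 26 days required between doses (6.1.8), injections in Weeks 1 to 6 at visits other than Week 4 add at most two more dipsticks. An occasional injection may be deferred.

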6.1.1 Identity of Investigational Product/New Drug

Monthly, injectable, buprenorphine extended-release (XRB, Sublocade™, Indivior) is the most recently FDA approved pharmacotherapy for opioid use disorders in the U.S.(2). XRB is available as of March-2018 in a pre-mixed subcutaneous formulation, administered monthly, and equivalent to a 16-24mg/day maintenance dose of sublingual buprenorphine-naloxone (SLB). Sublingual buprenorphine was approved by the FDA in 2002 and is delivered daily by placing the medication under the tongue for 5 to 10 minutes and letting it dissolve completely.

6.1.2 Dosage, Admin, Schedule

Buprenorphine Extended Release: XRB is a 300mg or 100mg pre-mixed subcutaneous injectable formulation to be administered monthly. XRB is for abdominal subcutaneous injection only. Participants in the XRB treatment arm will be given 1 or more XRB injections prior to release from jail and one or more at weeks 4, 8, 12, and 16 post-release, depending on their release date.

Sublingual Buprenorphine: SLB (SUBOXONE, Zubsolv, or generic tablets) is a daily sublingual film or tablet ranging from 8-24mg/day or equivalent (Zubsolv is dosed 5.7-17.1 mg/day). The film or tablet is placed under the tongue for 5 to 10 minutes until dissolved completely. Participants in the SLB treatment arm will be provided SLB daily by observed dosing in-jail (controlled substances are not self-administered in-jail) and encouraged to continue SLB treatment in weekly, bi-weekly, or monthly quantities for unobserved, daily, self-administration through week 5. Patients may obtain SLB care free-of-charge from the Bellevue Hospital Center Addiction Medicine clinic or from non-NYU/Bellevue providers and pharmacies per usual care standards. After the completion of Visit 5 Week 8, SLB participants will be offered XRB treatment in the 20 week therapeutic extension. If interested, participants would receive one or more XRB injections during the period of Weeks 8, 12, 16, 20, 24, and 28 followed by a final safety documentation visit at Week 32.

6.1.3 Method of Assignment/Randomization

Screening and Randomization

This pilot will recruit from within the standard-of-care NYC jail opioid treatment program, led by the program director, [name]. Potential participants currently maintained on sublingual buprenorphine (currently a NYC jail standard of care) will be offered study information and encouraged to enroll. Interested participants will be referred by the Opioid Treatment Program staff to Study Staff for further education about the trial and to schedule written informed consent and a comprehensive screening visit. Consented and eligible participants will be randomized by sealed envelope or a web-based randomizer 1:1 to the 2 study cells: XRB and SLB.

6.1.4 Blinding and Procedures for Unblinding

This is an 8-week, open-label, single site, proof-of-concept randomized controlled trial. There is no blinding of treatment assignment or of outcomes assessments.

6.1.5 Packaging/Labeling

Buprenorphine Extended Release (SUBLOCADE): XRB is available in dosage strengths of 100 mg/0.5 mL and 300 mg/1.5 mL buprenorphine. Each dose is provided in a prefilled syringe with a 19 gauge 5/8-inch needle. The recommended dose of XRB following induction and dose adjustment with transmucosal buprenorphine is 300 mg monthly for the first two months followed by a maintenance dose of 100 mg or 300mg monthly. We will offer both 300mg and 100mg doses pre-release and at week 4 post-release. Each dose is supplied in an individual kit and will be acquired in bulk shipments from the supplier Indivior.

At the outset of this study and original IRB approval, it was proposed that each participant randomized to the XRB (SUBLOCADE) treatment arm would receive up to two injections of XRB, each 300mg according to the medication package insert. However, the study has since been modified to include a therapeutic treatment extension of 24 additional weeks post Visit 5 Week 8 in which initial and/or additional XRB injections would be offered to all interested participants (see section 5.1.1). With this therapeutic extension, eligible & interested participants could receive 4+ XRB injections in the community. With this in mind, the study must expand the planned XRB dosage to include the 100mg formulation of XRB. As the XRB package insert states, the recommended dose of XRB following induction is 300mg monthly for the first two months followed by a maintenance dose of 100mg or 300mg monthly. The study must have the capability to offer eligible participants receiving a third XRB injection the lower, recommended maintenance dose of 100mg in addition to the standard 300mg.

Sublingual Buprenorphine (SUBOXONE, Zubsolv, or generic tablets): SLB is administered sublingually or buccally as a single daily dose. Medication should be prescribed in consideration of the frequency of visits. Provision of multiple refills is not advised in early treatment or without appropriate follow-up visits. After treatment induction and stabilization, the maintenance dose of SLB is generally in the range of 4mg/1mg buprenorphine/naloxone to 24mg/6mg buprenorphine/naloxone per day depending on the individual patient and clinical response, as determined by the clinician. Daily doses will vary by individual. The recommended target dose of SLB during maintenance is 16mg/4mg buprenorphine/naloxone. SLB will be prescribed and provided via observed dosing in-jail (controlled substances are not self-administered in-jail) per usual care protocols. Post-release, all participants may elect to continue SLB maintenance with the Bellevue Primary Care Addiction Medicine clinic, or may pursue SLB maintenance from non-NYU/Bellevue community providers. SLB is available free of charge to uninsured patients at Bellevue Hospital Center, or participants may fill SLB prescriptions at community pharmacies. SLB medication will not be provided by the study itself. Self-report, BHC EMR records, and NYS Prescription Monitoring Plan audits will document SLB post-release community treatment retention, daily dose, and refill frequencies.

